While extensive efforts are constantly undertaken to improve the capabilities of technology, such as imaging devices, to help detect, characterize and assess diseases, very limited efforts are undertaken to research systematically and analyze how environmental factors within healthcare facilities can influence and improve the experience of patients and staff. Patient motion, for example, is one of the sources of artifacts in imaging studies that may influence the quality, duration, and diagnostic certainty of imaging examinations. Patients are frequently confronted with recent unfavorable news about their health condition and are concerned about the outcome of imaging examinations and therefore may be especially receptive to positive or negative environmental factors and experiences.

The positive, calming, and relaxing impact of music has been well studied and recent questionnaire based assessments confirm that different light hues/colors lead to different experiences that can influence the overall feeling of person in a healthcare environment. A very important observation, however, is that those experiences are quite personal, and therefore, a wide variability of positive or negative perceptions to environmental stimuli are observed indicating that a personalization of those environmental stimuli might be the most effective approach.

Tremendous technological advances have occurred in recent years that enable readily controllable lights, sound, temperature, airflow as well as sensory experiences such as smell or vibrations. These technologies are used in virtual amusement rides or enhanced cinematic experiences; however, their potential application within healthcare environments, especially imaging environments, remains without systematic analysis.

With the availability of consumer grade wearable devices, continuous capturing of physiologic parameters such as heart rate, motion, body perspiration and muscle tension has become readily feasible.

Short wave radar can be used to detect motion and will be explored to detect positional changes and potential other physiological characteristics that may inform about a subject's state of being relaxed or active.

Using electronic capture devices such as tablets or smart phones combined with easily manageable tactile feedback or response capture capabilities to questions, scenes or videos, data about a

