Patients may be invited to participate if they are scheduled to get an imaging exam at the Wright Center facility. This means we would look at the schedule of patients expected for an imaging examination at the Wright Center of Innovation. When the imaging exam is scheduled or when they arrive at the facility patients may be asked if they are interested in participating in this research study. Very frequently we communicate prior to an imaging study with the patients, and we may make them aware that there is a possibility for them or also an accompanying person to participate in this research. We assume that we will also be informed from healthcare support staff of referring and collaborating healthcare providers that patients identified their interest to participate in the study. Frequently, patients also contact us as we are the communicated contact pathways identified on brochures and others posts and we will subsequently follow-up and discuss potential participation. Not every patient will be approached regarding this study, we will have to determine the feasibility in the schedule and determine if we have the staff on hand to complete the study, additionally, what imaging examination they get may also determine if at the time they can enroll in the study or not.

Administration of informed consent

Informed consent may be given at any time after the subject had appropriate time to read the informed consent form and ask and receive answers to any questions. As we anticipate that, for example, accompanying persons waiting for patients to complete their imaging study may be willing to participate in this study. Therefore, we may approach a subject immediately prior to the opportunity to participate especially as this is a minimal risk investigation. We have prepared a video that explains this trial to interested subjects. The video link may also be referenced in advertising material and brochures.

We prepared a training video for the trial staff to see how we would like to have the informed consent administered according to all aspects of GCP and applicable guidelines. There are different videos for each the patient, staff and volunteer populations.

The informed consent form may be given to subjects ahead of time. There will be online access to the informational video and the informed consent forms.

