Environmental Experience	
Lighting	
Sound	
Smell	
Vibration	
Temperature	
Voice activation	
Observational Tools	
Surveys	
Infrared Camera	
Radar	
Wearable device	

Location of performance of research

Due to the simplicity of the set up and straight forward design of this research it can be performed whenever subjects are available at the Wright Center facility; however, trained personnel will also have to be available.

While the patient related research efforts will be exclusively performed at the Martha Morehouse facility at The Ohio State University Wexner medical center, staff and volunteer environmental experience could be performed anywhere on the OSU campus or its affiliated facilities.

The online survey can be performed anywhere and the location will not be tracked.

Testing procedures and data recording

As we intend to develop research testing procedures tailored to the specific environmental experience or observational tools, we plan to refine the specific forms and assessment protocols in an iterative fashion during the initial phase that will include up to 25 subjects for each of the environmental experiences. The initial survey tools have been put in place and are available.

RP0525 Testing Procedure: Survey Tools

General Survey

The general survey that we intend to release via online social media for the public to take. This is the survey that will be openly accessible to the public and will be posted online for the virtual participation:

[**RP0525_EnvironmentalFactorsSurvey_SurveyMonkey.pdf**](#)

This can be accessed with the link: <https://www.surveymonkey.com/r/environmental-perception>

Study Survey

The survey tool that will be used to collect data from the subjects. Note that there is circular logic applied making sure all the data is combined into one database although no subject will actually complete every question.

[RP0525_EnvironmentalFactorsStudy_SurveyMonkey.pdf](#)

This can be accessed with the link:

https://www.surveymonkey.com/r/RP0525_EnvironmentalStudy

Imaging Assessment Survey

The survey completed by imaging assessors to determine the level of motion artefacts present in the images:

[RP0525_ImagingAssessmentSurvey_SurveyMonkey.pdf](#)

This can be accessed with the link:

https://www.surveymonkey.com/r/RP0525_ImagingAssessment

Incidental findings

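### Patients are approached at staff discretion and pooled with self-referred and referrer-relayed patients, and no described record would let the study assess the resulting selection.

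*Protocol*

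**What the plan says.** The Patient Population paragraph under Subject Recruitment (Protocol IV.B) describes three ways into the patient sample.

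- **From the imaging schedule.** "When the imaging exam is scheduled or when they arrive at the facility patients may be asked if they are interested". This is conditional: "Not every patient will be approached regarding this study, we will have to determine the feasibility in the schedule". Staff must also "determine if we have the staff on hand to complete the study", and "what imaging examination they get may also determine if at the time they can enroll in the study or not".
- **By self-referral.** "Frequently, patients also contact us as we are the communicated contact pathways identified on brochures and others posts".
- **Through referring providers.** The centre expects to be "informed from healthcare support staff of referring and collaborating healthcare providers that patients identified their interest to participate in the study".

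The section on the location of the research repeats the staffing condition: "trained personnel will also have to be available". No consecutive, sampled or otherwise pre-set approach rule is given.

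Two records are described. The identification document (Subject enrollment) holds name and contact details, and for patients the medical record number and referring physician. The audit and training log covers enrolled subjects, with who took consent and when.

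The Internal Validity section undertakes to assess sources of systematic error so that conclusions can be generalized. Its Selection bias entry names selection and self-selection as threats. The analysis is descriptive (IV.D, Data Analysis).

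**The concern.** In a descriptive study, who is in the sample largely determines the result. Here the patient sample comes from staff decisions made case by case, mixed with two other routes whose entrants may differ from approached patients and from each other. If any of these conditions or routes is related to how patients perceive the environment, the described perceptions differ systematically from those of the patients scheduled at the facility. Enrolling more patients under the same rule would not reduce that difference.

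The protocol recognises the threat but gives the study no means of examining it at the approach step. For other threats it names a concrete measure: training and observed sessions against bias from the person administering the experience, and device quality control against instrument change. For recruitment it names none. Without a count of patients not approached or declining, and without the entry route, the promised assessment of systematic error cannot cover selection into the patient group. The findings are meant to guide confirmatory trials, so the gap would carry forward.

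**Working it through.** **The plan's own figures.** Planned enrolment adds up: 125 staff + 125 patients + 250 volunteers = 500. The protocol anticipates 20% incomplete data or dropout, so 125 x 0.8 = 100 evaluable patients. That 100 is a back-calculation and is not stated. No figure in the plan quantifies selection: the share of eligible patients approached and any difference between approached and other patients are both absent. What follows is illustration on assumed ranges.

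**Illustration 1: a mean score, approached patients only.** Suppose a normally distributed tendency to be approached has correlation r with a perception score, and the fraction p with the highest tendency is approached. The shift in the mean, in SD units, is r x i, where i = phi(z)/p and z is the normal cut-off leaving p above it. Assume r from -0.3 to +0.3.

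| p | z | i | r = 0 | r = ±0.1 | r = ±0.2 | r = ±0.3 |
|---|---|---|---|---|---|---|
| 0.3 | 0.524 | 1.159 | 0 | ±0.12 | ±0.23 | ±0.35 |
| 0.1 | 1.282 | 1.755 | 0 | ±0.18 | ±0.35 | ±0.53 |

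For scale, the 95% half-width of a mean with 100 patients is 1.96/√100 = 0.196 SD. Part of the assumed range lies below sampling error and part above it.

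These shifts do not describe the whole enrolled sample. If a share w of enrolled patients was approached and the rest have their own shift s, the overall shift is w x (r x i) + (1 - w) x s. The protocol gives neither w nor s.

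**Illustration 2: a proportion.** Let f be the share of eligible patients who can be approached and d the difference in response between them and the others. The bias is b = (1 - f) x d. At a proportion of 0.5 with n = 100, SE = √(0.25/100) = 0.05, so the 95% half-width is 9.8 points. Coverage of a nominal 95% interval is Phi(1.96 - b/SE) - Phi(-1.96 - b/SE), which is the same for either sign of d.

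| f | d (points) | bias (points) | coverage |
|---|---|---|---|
| any | 0 | 0 | 95% |
| 0.7 | ±10 | ±3 | 91% |
| 0.5 | ±10 | ±5 | 83% |
| 0.3 | ±20 | ±14 | 20% |

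**Effect on spread, for Aim 3.** Under the model of illustration 1, the variance of the score falls by r² x i x (i - z). At the extreme used (r = ±0.3, p = 0.1) this is 0.09 x 1.755 x (1.755 - 1.282) = 0.075. Variance falls by about 7.5% and the SD by about 4%.

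**What the records could show.** Consent dates, medical record numbers and the imaging schedule would allow partial reconstruction of examination type and workload for enrolled visits. They would not show who was passed over and why, who declined, or by which route an enrolled patient came.

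**The case against.** The strongest reply is that convenience sampling is ordinary in an exploratory, descriptive study meant to guide later trials, and that the protocol openly names selection and self-selection as threats. That limits the consequence. It does not supply the information needed to assess the threat, which the protocol itself undertakes to do.

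A second reply is that some records can be reconstructed, and that the study survey and data bank forms are named but their content is not shown. This stands in part. The gap is confined to non-approach, refusal and entry route, and it is a gap in what the protocol describes.

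A reader might infer that the sample leans toward calm patients on uncrowded visits. The documents do not support that. None of the three stated conditions concerns a patient's demeanour. Patients may be asked when the examination is scheduled, before any distress on arrival could be seen. A delayed list could lengthen waiting and make approach easier, and self-referrers could be more anxious than others. The Background remark that patients "therefore may be especially receptive to positive or negative environmental factors and experiences" is about patients generally and picks out no worried subgroup that recruitment would miss.

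A reader might also infer that Aim 3 loses much of the range of anxiety or motion. On the model above the SD falls by about 4% at the extreme, which is negligible. Examination type still matters for Aim 3 as a question of sample composition, because motion artefact may differ between modalities.

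**Conclusion.** The concern holds in a limited form. The protocol fixes a discretionary approach rule, mixes its entrants with two other routes, and describes no record from which the selection could be assessed. The patient descriptions are therefore at risk of selection bias whose direction and size cannot be determined from the documents.

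On the assumed ranges the bias runs from nil to 0.35 SD (30% approached) or 0.53 SD (10% approached) in either direction, for approached patients only. On the proportion scale it runs from nil to 14 points in either direction. The correlation, the fraction approached and the response difference are all assumptions, and if approach is unrelated to perception there is no bias.

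The point does not depend on any particular value. It rests on the absence of an approach rule and of the records needed to examine its effect. No sample size figure changes.

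**What to change.** 1. Set recruitment sessions in advance from the staffing roster. Within a session, approach eligible scheduled patients in schedule order as far as capacity allows.
2. From the schedule that staff already view, keep a de-identified tally, by examination type, of patients scheduled, not approached (with the reason), declined and enrolled. Examination types that cannot be enrolled at the time are counted with that reason.
3. Record each enrolled patient's entry source: approached in a session, self-referred, or interest relayed by a referring provider's staff.
4. Describe patient results by entry source and by examination type, alongside the tally.

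The cost is slightly less flexible accrual, a session calendar, a tally sheet and one extra field. Because approach is limited to existing capacity, the rule does not itself require more staff. Sessions placed by staff availability still select which visits can contribute: the rule reduces discretion within a session but does not remove selection by session. The protocol should state that as a limitation.

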We will explore the use of wearable devices like Fitbit, Apple Watches, and Samsung Gear Fit devices, which allow the recording of motion and heart rate. Specifically, the following devices may be used during the study: Fitbit Flex 2, Fitbit Alta, Fitbit Alta HR, Fitbit Charge 2, Apple Watch Series 3, Samsung Gear S3, Samsung Gear S4, Samsung Wing, Samsung Gear Edge. Since this is an exploratory study, we will assess the feasibility of using these devices within the study's methodological parameters. This will allow us to determine which devices to use in the experimental trials.

These devices will be placed on the subject at their preferred wrist location and will be removed before leaving the facility. We hypothesize for example that tracking the pulse rate will be an indirect measure of the subjects' excitement level and may also be a ready measurement of the likelihood of motion during an examination. These wearable devices will not be used during the MRI imaging examination.

B. Detailed study procedures

Subject enrollment

As detailed already above, there will be three different populations enrolled in this study, volunteer, staff, and patients. All subjects will sign an informed consent form, and patients are additionally asked to sign a HIPAA waiver.

As part of the informed consent process, the subject identification document will be created that will identify the subject name and current contact information.

In case of patients, their medical record number, referring physician for the imaging procedure performed and contact information of a healthcare provider of their choice if they indicated that any incidental finding should be communicated directly to their healthcare provider, will be recorded.

This document will also record if the subject received a gift card and the amount.

The subjects participating in this research **may be enrolled at multiple times** and can also be involved in multiple subject categories. Multiple enrollment may occur for the purpose of longitudinal observations or assessment after healthcare treatments. The initial and follow up responses may be evaluated regarding changes over time.

Subject Recruitment

Virtual participation only

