For participants on the online survey only (virtual participation), an online consent script will precede the survey. There will be no further consenting in this population.

RP0525 Audit Log and Training Log

This audit and training log provided will be used to keep track who has been trained to do the informed consent, complete the proper procedure for this study, as well as administer the wearable devices for this particular study and by whom. Additionally, this document keeps track of the subjects involved in the study and who administered the informed consent to them and when.

RP0525_Adjunctive_Data_Bank_Forms_V02.xlsx

Withdrawal from the study

A subject can withdraw at any time from the study. At the time of a potential withdrawal the subjects may be asked if he or she wants to do a complete withdrawal or just wants to stop further participation and allows the gathered data to be used. This option would only be applicable if the subject participates in the facility environmental experience.

Compensation for participation in the research

Volunteers and patients who participate in the physical environmental experience will receive a gift card of \$20 - \$50 gift card depending on their time commitment to the study.

Virtual participants who have only completed the online survey are only eligible to be entered from a raffle gift card.

Staff of the Department of Radiology and the Wright Center of Innovation will not be eligible for compensation for participation in this research, the time spent participating may be considered to be part of work time.

Subjects have the opportunity to decline the acceptance of the gift card or can designate that the value of the gift card would be donated to the Wright Center of Innovation in Biomedical Imaging development fund. A decline or designation to donate does not lead to any taxable events.

Gift card of \$20 value

Completion of a survey tool and participation in environmental testing of less than 30 minutes.

Gift card of \$30 value

Completion of a survey tool and participation in environmental testing of more than 30 minutes.

Gift card of \$50 value

Completion of multiple survey tools and participation in extensive environmental testing exceeding an active participation time period of more than 60 minutes.

Raffle Gift Card

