Participants who have completed the general online survey by a specific date will have the opportunity to submit their email address at the end of the survey to be entered into a raffle for a chance to win one of five \$20 gift cards. This email will only be kept on record to determine the winners and will not be linked to their answers to the survey. These winners will be selected at random using a random number generator and will then be emailed to the winning participants after the date indicated on the survey.

Enrollment and participation choices**Online survey tool (virtual participation)**

As this survey will be openly accessible, we will not place any restriction on the number of participants but plan to close the survey once we have reached 1000 responses. We would like to achieve a broad participation and would be delighted to have responses in the range of 100 – 1000. This survey is identified below and labeled as the general survey.

Environmental experience (physical participation)

We anticipate a 20% rate of incomplete data or dropouts, so we request an initial total enrollment approval of 500 subjects. Of the 500 subjects, we intend to enroll 125 staff members, 125 patients, and 250 volunteers. We intend to use survey tools to assess the perception and preference of different environmental components. Subjects may participate in multiple experiences within a single session.

Subject participation choices

Subjects will be classified according to their type of participation into the three categories of volunteer, OSU staff or patients. In order to be eligible for the study, all subjects must complete an informed consent form. Patients, additionally, may complete the imaging examination experience during their imaging procedure. The table below summarizes the options given to the subject and reflects those that are included in the informed consent form.

Dependent on the implementation and testing set up available, subjects will be given the choice to participate in up to six environmental experiences. While the research staff will identify to the subject which environmental experience will be available, subjects have the choice to only select those in which they are willing to participate.

In addition to the survey tools, we will be potentially using additional observational tools such as infrared camera, radar and or wearable devices.

Subject Type	Participation
Volunteer	
WCIBMI Staff	
Patient	
Choices	
Survey only	
Facility Experience	

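### Does the open online survey, with its raffle and unlinked e-mail address, need a written rule against repeat submissions?

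*Protocol*

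**What the plan says.** The protocol treats the general survey as an anonymous, open instrument.

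- **Access** (RP0525 Testing Procedure: Survey Tools, General Survey): "This is the survey that will be openly accessible to the public and will be posted online for the virtual participation".
- **Size and closure** (Online survey tool, virtual participation): "we will not place any restriction on the number of participants but plan to close the survey once we have reached 1000 responses". The investigators add that they "would be delighted to have responses in the range of 100 – 1000".
- **Raffle** (Raffle Gift Card): people who complete the survey by a set date "will have the opportunity to submit their email address at the end of the survey to be entered into a raffle" for one of five $20 cards. On that address: "This email will only be kept on record to determine the winners and will not be linked to their answers to the survey".
- **Location** (Location of performance of research): "The online survey can be performed anywhere and the location will not be tracked".
- **Consent** (Administration of informed consent): "an online consent script will precede the survey. There will be no further consenting in this population".

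The Subject enrollment section allows people to be enrolled more than once "and can also be involved in multiple subject categories". The Survey tools section gives the survey's purpose as a broad impression of public feeling. Both data analysis sections plan descriptive statistics, and the earlier one also commits to statistical advice on how data are captured and tabulated. No one-response rule, one-entry rule or duplicate check is written down.

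**The concern.** Put together, these rules look unfortunate. Anyone can open the link, a completed form leads to a possible prize, and the survey stops on forms, not people. The e-mail address is the only identifier described for virtual participants. It is optional and is kept apart from the answers. A repeated address in the raffle list could show that someone entered twice, but not which answers to drop.

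If repeats were common, three things would suffer. The reported number would exceed the number of people, part of the 1000-response allowance would be used up, and percentages could move towards the views of those who resubmit. The internal validity discussion names self-selection in online surveys but does not mention duplicate submission.

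**Working it through.** **1. The plan's own figure.** The 1000-response cap has no stated derivation: no precision, power or error rate is given for the survey. There is nothing to reproduce, and no stated figure is shown to be wrong.

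**2. Are repeats allowed?** The multiple-enrolment text in Subject enrollment concerns subjects who sign a consent form and have an identification document, and its stated purpose is longitudinal observation. Virtual participants see only a consent script. The words "and can also be involved in multiple subject categories" concern someone who is, for example, both staff and volunteer. For repeat responses to the public survey, the protocol is silent.

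**3. Are duplicates beyond control?** The e-mail route is closed. The protocol refers to a survey file and a hosted link, but neither the file nor the platform settings are shown. A limit of one response per device would need no link to the e-mail, and it may already be switched on. The location sentence says where the survey may be taken; it does not say that device controls are off.

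**4. How strong is the incentive?** Inputs from the protocol: five prizes of $20 and 100 to 1000 responses. Assumption: every response enters the raffle. For k entries among R, the chance of at least one prize is 1 − C(R−k, 5)/C(R, 5). The expected value of one entry is 5 × $20 / R.

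| R | One entry | Value of one entry | Five entries |
|---|---|---|---|
| 1000 | 0.5% | $0.10 | 2.5% |
| 100 | 5.0% | $1.00 | 23.0% |

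Repeating raises the odds almost in proportion, but from a small base.

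**5. What would duplicates do?** The documents give no duplicate rate. The shares below are assumptions, for scale only.

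*People behind the count.* With 5%, 10% or 20% surplus copies, 1000 responses come from 950, 900 or 800 people.

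*Precision.* Weight each person by the number of copies submitted, so that n_eff = R² / (sum of squared weights). Take R = 1000.
- 5% surplus, two copies per repeater: 900 single responders and 50 repeaters. n_eff = 1000² / (900 + 50 × 4) = 909.
- 20% surplus, five copies per repeater: 750 single responders and 50 repeaters. n_eff = 1000² / (750 + 50 × 25) = 500.

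The 95% half-width at p = 0.5 is 1.96 × √(0.25/n). This gives 3.1 points nominally (n = 1000), 3.3 points at 909 and 4.4 points at 500. Coverage of a nominal 95% interval would be 93.8% and 83.4%. At 100 responses the same two cases give 10.3 and 13.9 points against a nominal 9.8.

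*Bias.* Shift = duplicate share × (proportion among duplicates − proportion among unique respondents). With an assumed 90% against 60%, the shift is 0.05, 0.10 or 0.20 × 30 = 1.5, 3.0 or 6.0 points. If duplicates answer like everyone else, the gap and the shift are both zero.

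**6. Do those sizes bear on a planned use?** The half-widths presume random sampling, which a self-selected social-media survey does not offer and the protocol does not claim. The analysis is descriptive. Anything from 100 to 1000 responses is welcome, so places lost to duplicates defeat no target.

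**The case for a change.** The best case for a change is about timing. Duplicate control belongs to data capture. The protocol itself fixes the raffle, the stopping count and the separation of e-mail from answers, and a later analysis plan can clean only what was collected. The link is to be released on approval, so a control has to be in place by then. The protocol promises continual attention to sources of bias and allows data to be shared or made public, so an inflated count could travel. A setting and two sentences would be cheap, and the answers could stay anonymous.

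Part of this stands. No control is written down, the e-mail cannot serve as one, and a count of responses should not be read as a count of people.

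The rest does not make a defect. The suggested remedy leaves the e-mail separation, the raffle and the public link as they are, which shows that none of those rules is wrong in itself. It adds a platform setting that may already exist. The remedy is also imperfect: a device is not a person, so a count of unique respondents still could not be verified. Surveys may also be offered on tablets at the facility, where a per-device limit could turn away genuine respondents if the general survey is used there.

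**Conclusion.** No change to the protocol is needed. The observation is accurate as far as it goes: the open survey counts responses, offers a raffle, keeps the only identifier it describes away from the answers, and states no duplicate control. What is left is an unwritten operational detail, and the planned statistical review of data capture and tabulation is a natural place to settle it. Describing the total as responses is enough for the survey's purpose.

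The consequence is modest. At the cap, an entry is worth about $0.10 if everyone enters. Under assumed surplus shares of 5% to 20%, the half-width would be 3.3 to 4.4 points instead of 3.1, in a survey that claims no precision. The shift of 1.5 to 6.0 points also needs an assumed 30-point difference in opinion, for which the documents give no basis. The conclusion rests on the survey remaining exploratory and descriptive. It would need another look if the survey percentages were later used for formal inference or as a count of distinct people.
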